9.7.8. Week 9 through Week 48 (Safety Contact)

Patients should be contacted by telephone/email at Week 9 and every 3 weeks afterward to Week 48.

- Contact patient by phone/email.
- Review and record prior concomitant medications.
- Assess and record AEs.
- Review and record any non-study related medical or surgical treatment procedures and any medically relevant HCP or non-HCP related office visits that have occurred since the previous study visit.
- Assess investigational product compliance, perform investigational product accountability.

9.7.9. Week 12, Week 24, Week 36 Procedures

- Verify that the patient has fasted for at least 8 hours.
 - Record fasting status in the source and eCRF
 - If the patient reports having eaten within 8 hours, document accordingly in the source and eCRF and remind the patient that fasting is required prior to all study visits, but water is permitted.
- Assess and record vital signs and weight (oral temperature, sitting heart rate, respiratory rate, and sitting blood pressure).
- Assess and record AEs.
- Perform a physical examination.
- Review and record any non-study related medical or surgical treatment procedures and any medically relevant HCP or non-HCP related office visits that have occurred since the previous study visit.
- Review and record concomitant medications.
- Perform assessments for calculation of CP Score ([Section 14.1.1](#)).
- Administer Quality of Life and Patient questionnaires (see [Section 13.2.7](#)).
- Assess investigational product compliance, perform investigational product accountability.
- Assess for dose titration, if eligible. (Refer to [Section 7.3](#))
- Dispense investigational product only if there is dose increase or as needed. No new investigational product bottles will be dispensed if there is only change in dosing frequency of the same dose level. Patients are expected to use up each investigational product bottle before a new bottle will be dispensed.
- Perform a urine-based β -hCG pregnancy test in females of childbearing potential.
- Obtain blood samples for
 - Serum chemistry, hematology, and coagulation
 - Markers of fibrosis (ELF [HA, P3NP, and TIMP 1])
 - Bile Acid/C4/FGF-19
 - Fasting PK assessment (**Week 36 only**)
- Perform TE using the Fibroscan[®] TE device. If the TE cannot be performed on visit day (eg, device/technician unavailability, scheduling issues, TE data is needed to inform cirrhosis assessment, etc.), the procedure may be completed within the visit window (if data is needed for cirrhosis assessment) or as close as possible to the visit.
- Perform an ultrasound for HCC surveillance at **Week 24 ONLY** (if equipment is unavailable, sites should make every attempt to use available community referral sites).

- Serial PK assessment **at Week 12 and 24 ONLY (not done at Week 36)**; the following procedures will be conducted in all patients:
 - 30 minutes prior to dosing: collect predose blood sample
 - Dispense/Administer investigational product from the double-blind bottle (collected from the patient upon arrival for this visit) with 240 mL (8 oz.) of water. Instruct the patient to swallow the tablet whole; s/he must not chew, divide, or crush the tablet.
 - Collect blood samples at: 30 min, 45 min, 1 hour postdose
 - Immediately following 1 hour postdose blood draw, administer meal replacement drink (to be consumed within 5 – 10 minutes)
 - Collect blood samples at: 1.5, 2, 2.5, 3, 4, 5, 6, 7, 8, 9, and 24 hours post dose

Note: Patients should not drink additional water for 1 hour after taking the dose of investigational product and will remain fasted until after the 1-hour sample is collected. A meal replacement drink will be provided following collection of the 1-, 4-, and 7-hour PK sample. No other food or drink (water is permitted) will be allowed until after the 9-hour sample collection (see [Figure 4](#)). The 24-hour post-dose sample can be obtained upon return to the clinic or by a home health care designee.

- Schedule the next visit, reiterate dosing instructions, and advise the patient:
 - NOT to take investigational product on the morning of the next visit, and
 - To bring the investigational product bottle(s) to visits; s/he will dose at the clinic for Week 18 and Week 30 visits (if this is in compliance with the established dosing frequency), and
 - To fast overnight (at least 8 hours) prior to the next visit. Fasting is required prior to all study visits, but water is permitted.

9.7.10. Week 18 and Week 30 Procedures

- Verify that the patient has fasted for at least 8 hours.
 - Record fasting status in the source and eCRF.
 - If the patient reports having eaten within 8 hours, document accordingly in the source and eCRF and remind the patient that fasting is required prior to all study visits, but water is permitted.
- Perform a physical examination.
- Review and record any non-study related medical or surgical treatment procedures and any medically relevant HCP or non-HCP related office visits that have occurred since the previous study visit.
- Assess and record vital signs and weight (oral temperature, sitting heart rate, respiratory rate, and sitting blood pressure).
- Assess and record AEs.

- Review and record concomitant medications.
- Perform assessments for calculation of CP Score ([Section 14.1.1](#)).
- Administer Quality of Life and Patient questionnaires (see [Section 13.2.7](#)).
- Assess investigational product compliance, perform investigational product accountability.
- Assess for dose titration, if eligible (refer to [Section 7.3](#)).
- Dispense investigational product only if there is dose increase or as needed. No new investigational product bottles will be dispensed if there is only change in dosing frequency of the same dose level. Patients are expected to use up each investigational product bottle before a new bottle will be dispensed.
- Perform a urine-based β -hCG pregnancy test in females of childbearing potential.
- Obtain blood samples for
 - Serum chemistry, hematology, and coagulation
 - Bile Acid/C4/FGF-19
- Serial PK assessment; the following procedures will be conducted in all patients:
 - 30 minutes prior to dosing: collect predose blood sample
 - Dispense/Administer investigational product from the double-blind bottle (collected from the patient upon arrival for this visit) with 240 mL (8 oz.) of water. Instruct the patient to swallow the tablet whole; s/he must not chew, divide, or crush the tablet.
 - Collect blood samples at: 30 min, 45 min, 1 hour postdose
 - Immediately following 1 hour postdose blood draw, administer meal replacement drink (to be consumed within 5 – 10 minutes)
 - Collect blood samples at: 1.5, 2, 2.5, 3, 4, 5, 6, 7, 8, 9, and 24 hours postdose

Note: Patients should not drink additional water for 1 hour after taking the dose of investigational product and will remain fasted until after the 1-hour sample is collected. A meal replacement drink will be provided following collection of the 1-, 4-, and 7-hour PK sample. No other food or drink (water is permitted) will be allowed until after the 9-hour sample collection (see [Figure 4](#)). The 24-hour post-dose sample can be obtained upon return to the clinic or by a home health care designee.

- Schedule the next visit, reiterate dosing instructions, and advise the patient:
 - NOT to take investigational product on the morning of the next visit, and
 - To bring the investigational product bottle(s) to both visits; s/he will dose at the clinic on Week 24 (if this is in compliance with the established dosing frequency), and
 - To fast overnight (at least 8 hours) prior to the next visit. Fasting is required prior to all study visits, but water is permitted.

9.7.11. Week 48 Procedures

- Verify that the patient has fasted for at least 8 hours.
 - Record fasting status in the source and eCRF
 - If the patient reports having eaten within 8 hours, document accordingly in the source and eCRF and remind the patient that fasting is required prior to all study visits, but water is permitted.
- Perform a physical examination, including smoking and alcohol consumption history, and current habits for both.
- Review and record any non-study related medical or surgical treatment procedures and any medically relevant HCP or non-HCP related office visits that have occurred since the previous study visit.
- Assess and record vital signs and weight (oral temperature, sitting heart rate, respiratory rate, and sitting blood pressure).
- Assess and record AEs.
- Review and record concomitant medications.
- Perform ECG.
- Perform assessments for calculation of CP Score ([Section 14.1.1](#)).
- Administer Quality of Life and Patient questionnaires (see [Section 13.2.7](#)).
- Assess investigational product compliance, perform investigational product accountability.
- Assess for dose titration, if eligible (refer to [Section 7.3](#)).
- Dispense investigational product only if there is dose increase or as needed. No new investigational product bottles will be dispensed if there is only change in dosing frequency of the same dose level. Patients are expected to use up each investigational product bottle before a new bottle will be dispensed.
- Perform urinalysis
- Perform a urine-based β -hCG pregnancy test in females of childbearing potential.
- Obtain blood samples for
 - Serum chemistry, hematology, and coagulation
 - Markers of fibrosis (ELF [HA, P3NP, and TIMP 1])
 - Bile Acids/C4/FGF-19
- Serial PK assessment; the following procedures will be conducted in all patients:
 - 30 minutes prior to dosing: collect predose blood sample

- Dispense/Administer investigational product from the double-blind bottle (collected from the patient upon arrival for this visit) with 240 mL (8 oz.) of water.
- Collect blood samples at: 30 min, 45 min, 1 hour postdose
- Immediately following 1 hour post dose blood draw, administer meal replacement (to be consumed within 5 – 10 minutes)
- Collect blood samples at: 1.5, 2, 2.5, 3, 4, 5, 6, 7, 8, 9, and 24 hours post dose

Note: Patients should not drink additional water for 1 hour after taking the dose of investigational product and will remain fasted until after the 1-hour sample is collected. A meal replacement drink will be provided following collection of the 1-, 4-, and 7-hour PK sample. No other food or drink (water is permitted) will be allowed until after the 9-hour sample collection (see [Figure 4](#)). The 24-hour post-dose sample can be obtained upon return to the clinic or by a home health care designee.

- Perform TE using the Fibrosan[®] TE device. If the TE cannot be performed on visit day (eg, device/technician unavailability, scheduling issues, TE data is needed to inform cirrhosis assessment, etc.), the procedure may be completed within the visit window (if data are needed for cirrhosis assessment) or as close as possible to the visit.
- Perform an ultrasound for HCC surveillance (if equipment is unavailable, sites should make every attempt to use available community referral sites).
- Schedule the next visit, reiterate dosing instructions, and advise the patient:
 - NOT to take investigational product on the morning of the next visit, and
 - To bring the investigational product bottle(s) to the visit, and
 - To fast overnight (at least 8 hours) prior to the next visit. Fasting is required prior to all study visits, but water is permitted.

9.7.12. Every 3 Months after Week 48

Quarterly

- Verify that the patient has fasted for at least 8 hours.
 - Record fasting status in the source and eCRF
 - If the patient reports having eaten within 8 hours, document accordingly in the source and eCRF and remind the patient that fasting is required prior to all study visits, but water is permitted.
- Perform a physical examination, including height, smoking and alcohol consumption history, and current habits for both.
- Review and record any non-study related medical or surgical treatment procedures and any medically relevant HCP or non-HCP related office visits that have occurred since the previous study visit.

- Assess and record vital signs and weight (oral temperature, sitting heart rate, respiratory rate, and sitting blood pressure).
- Assess and record AEs.
- Review and record concomitant medications.
- Perform assessments for calculation of CP Score ([Section 14.1.1](#)).
- Administer Quality of Life and Patient questionnaires (see [Section 13.2.7](#)).
- Assess investigational product compliance, perform investigational product accountability.
- Assess for dose titration, if eligible (refer to [Section 7.3](#)).
- Dispense investigational product only if there is dose increase or as needed. No new investigational product bottles will be dispensed if there is only change in dosing frequency of the same dose level. Patients are expected to use up each investigational product bottle before a new bottle will be dispensed.
- Perform a urine-based β -hCG pregnancy test in females of childbearing potential.
- Obtain blood samples for
 - Serum chemistry, hematology, and coagulation
- Schedule the next visit, reiterate dosing instructions, and advise the patient:
 - NOT to take investigational product on the morning of the next visit, and
 - To bring the investigational product bottle(s) to the visit, and
 - To fast overnight (at least 8 hours) prior to the next visit. Fasting is required prior to all study visits, but water is permitted.

Patients will complete a TE/ELF (HA, P3NP and TIMP 1) and ultrasound (for HCC surveillance) assessment, every 6 months (± 2 weeks) after Week 48.

ECG and urinalysis will be done yearly (± 2 weeks) after Week 48.

9.7.13. End of Study/Early Termination/End of Treatment Procedures for Patients That Withdraw from Investigational Product or Withdraw Consent

Patients who discontinue investigational product before Week 48 are expected to continue in the study until the end of the study (EOS [when patient terminates the study]) or at the discretion of the Sponsor.

EOT (when patient discontinues investigational product)/ET procedures will be required whenever patients discontinue treatment with investigational product ([Table 1](#), [Section 9.7.11](#)). The EOT/ET Visit ([Table 1](#)) and procedures listed below ([Table 6](#)) must be performed as close as possible to the patient's last dose of investigational product. When a patient discontinues or interrupts investigational product and continues with regularly scheduled study visits, the EOS Visit will be completed as the patient's final study visit. The actual investigational product discontinuation scenario ([Table 6](#)) will determine the sequence of the EOT/ET and EOS Visits

and procedures. In some cases, the EOT/ET Visit and procedures will precede the EOS Visit; in others, the EOT/ET and EOS Visits will be combined and performed as close as possible to the patient's last dose of investigational product. EOT and EOS Visits are encouraged but at no time will a missed EOT or EOS visit be considered a protocol deviation.

When a patient ends her/his participation in the study (eg, at a point between standard study visits) either due to early termination (ET) (withdrawal of consent) or discontinuation, an EOT/EOS Visit must be performed as near as possible to her/his last dose of investigational product and the procedures listed in [Table 1](#) performed. The purpose of this visit is to conduct complete and/or final assessments on or as near as possible to the final day of dosing. In some cases, the patient may discontinue on the day of a scheduled study visit. In these cases, EOT/EOS Visit procedures should be performed in place of the scheduled study visit procedures. The data will be recorded as EOT/ET and EOS procedures in the eCRF.

Table 6: Early Discontinuation Scenarios

	Investigational Product	Consent	Study Visit Status	EOT Visit ^a	EOS Visit ^a
Early Termination	Discontinued	Withdrawn	No additional visits except EOT/EOS	Combined visit, completed as close as possible to last dose of investigational product.	
Treatment Discontinuation^b	Discontinued	Active	Regular Visit Schedule	Complete as close as possible to last dose of investigational product.	Complete at final study visit.
	Discontinued	Record review only	Record review only	Combined visit, completed as close as possible to last dose of investigational product.	
Sponsor Termination	Discontinued	N/A	No additional visits except EOT/EOS	Combined visit, completed as close as possible to last dose of investigational product.	
Pregnancy	Discontinued	Complete per the above scenarios - Early Termination or Treatment Discontinuation			
Lost to Follow-Up	Discontinued	LTF	None	Unable to complete due to LTF status	

EOS = end of study; EOT = end of treatment; LTF = lost to follow-up

^a Refer to [Section 7.1.2](#), Schedule of Study Procedures for all procedures and evaluations required at the EOS and EOT Visits.

^b Includes initiation of commercially available OCA.

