7. INVESTIGATIONAL PLAN

7.1. Overall Study Design

This Phase 4, randomized, double-blind, placebo-controlled study will evaluate the PK and safety of OCA treatment in patients with PBC and moderate to severe hepatic impairment defined as CP-B and CP-C including a broad distribution of MELD scores (ranging from 6 to 24). Approximately 50 patients (including at least 20% of patients with CP-C) will be enrolled in the study. Patients will be screened ≥ 14 days but not more than 28 days prior to entering the study (Day 1). Patients who meet all eligibility requirements will be randomized in a 1:1 ratio to 1 of 2 treatment groups: Placebo or OCA. Randomization will be stratified by CP class. Baseline MELD scores will be monitored on an ongoing basis to ensure adequate distribution of MELD scores.

[figure not shown]
Following completion of safety assessments and laboratory specimen collection, blinded investigational product will be dispensed with instruction to begin dosing the same day (Day 1) at OCA 5 mg or placebo once weekly.

Double-Blind Treatment Period: During the 48-week treatment period, an initial safety visit will occur at Week 3. After the Week 6 Visit, subsequent clinic visits will occur approximately every 6 weeks for the assessment of safety, tolerability, PK, and PD. Titration may be considered as early as the Week 12 Visit (see [Section 7.3](#)). Fasting PK assessments will be performed in all patients participating in the study on Day 1, Week 6, and Week 36. Serial PK sampling (which also includes a fasted PK assessment) will be performed at Week 12, 18, 24, 30, and 48.

Patients who have completed their 48-week, double-blind treatment period will continue double-blind treatment until all randomized patients have completed their 48-week treatment period and the database for that period is locked. An open-label extension study in which all patients receive OCA will be considered following review of blinded safety and PK data.

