AE = adverse event; eCRF = electronic case report form; C4 = 7α hydroxy-4-cholesten-3-one; CLDQ = Chronic Liver Disease Questionnaire; ELF = enhanced liver fibrosis; ET = Early Termination; EOS = End of study; EOT = End of Treatment; ; FGF-19 = fibroblast growth factor-19; HA = hyaluronic acid; HCV = Hepatitis C virus; IP = Investigational Product; P3NP = procollagen 3 N-terminal peptide; PBC = primary biliary cirrhosis; PK = pharmacokinetics; TE = transient elastography; wk(s) = week(s), TIMP-1 = tissue inhibitor of metalloproteinase ; VAS = Visual Analogue Scale.

^a Visit schedule should be based on Day 1. Day 1 visit must occur at least 2 weeks after screening visit.

^b Patients should be contacted by telephone/email every 3 weeks (±1 week) between clinic visits starting at Week 9 and continuing to Week 48 to assess for AEs, concomitant medications, medical/surgical procedures, and verify that s/he is dosing as directed. (see [Section 9.7.8](#)).

^c Preferably, the patient comes in to the clinic for this visit. Alternatively, site will telephone the patient for assessments and a home health nurse will visit to draw safety labs.

^d Visit should occur 3, 4, or 5 days after taking the Week 6 dose.

- ^e The patient should be instructed to fast overnight (at least 8 hours) prior to each visit. Fasting is required prior to all study visits, including screening, but water is permitted.
- ^f Height and assessment of smoking and alcohol consumption history and current habits will be assessed at Screening and Week 48. Assessment of smoking and alcohol consumption history and current habits will be assessed quarterly after Week 48.
- ^g Child-Pugh Score will be calculated based on ascites assessment, hepatic encephalopathy grade, and central laboratory evaluations per the Child-Pugh scoring system noted in the eCRF.
- ^h The EQ-5D-5L Quality of Life questionnaire is validated for use in multiple languages. If a validated translation is not available in the local language required for a specific study patient, the questionnaire will not be collected. The CLDQ measures change over time in patients with chronic liver disease.

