- ⁱ New investigational product bottles will be dispensed if the patient is up-titrated. Unless up-titrated, patients are expected to use up each investigational product bottle before a new bottle will be dispensed. No new bottles will be dispensed if dose frequency is changed. Patients will be instructed to begin dosing on Day 1, after completing all study assessments. Patients will be instructed to take investigational product at approximately the same time of day. Patients must be instructed to swallow the tablet whole; they must not chew, divide, or crush the tablet.
- ^j Dose titration of investigational product may occur starting after the Week 12 Visit, or any study visit thereafter for patients on all dosing regimens, based on tolerability and safety laboratory tests from the previous visit. Subsequent dose titration(s) may occur no earlier than 6 weeks after the previous dose titration and will be based on tolerability.
- ^k Urine β -hCG pregnancy tests must be performed in females of childbearing potential prior to entry and at every visit (except Week 3). If positive, a confirmatory blood test must be performed at the central laboratory. If the confirmatory blood test is also positive, the patient may not continue in the study. (Additional testing may be conducted where required, regionally).
- ^l MELD values will be calculated based on serum chemistry and coagulation values at each visit.
- ^m The patient will be given the option to return to the clinic the following morning for the 24-hour postdose PK sample or samples can be obtained by a home health care designee. Patients who are discontinued from investigational product prior to completion of the study are encouraged to continue to follow the regular visit schedule, with the exception of PK sampling.
- ⁿ The noninvasive radiological liver fibrosis measurement devices (such as, FibroScan[®] device [Echosens; Paris, France]) will be used at all study sites to collect hepatic stiffness measurements.
- ^o Patients will complete a TE/ELF and ultrasound assessment, every 6 months (± 2 weeks) after Week 48.
- ^p ECG and urinalysis will be done yearly (± 2 weeks) after Week 48 Visit.
- ^q Ultrasound will be conducted to enhance HCC surveillance. For all on study (eg, post-Day 1) ultrasounds: Unless HCC has already been confirmed by biopsy, a second confirmatory image (eg, MRI) should be obtained to confirm suspected HCC.

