7.4.2. Liver Biochemistry Assessments for Potential Hepatic Injury or Hepatic Decompensation

[figure not shown]
Liver biochemistry will be assessed to evaluate biochemical triggers that will prompt an immediate reevaluation of patients for potential hepatic injury or hepatic decompensation. These assessments will be performed at:

- Each protocol-specified visit (Table 1)
- Unscheduled visits as needed in the event of signs or symptoms of suspected hepatic injury or decompensation or if laboratory alerts have been triggered

It is important that the laboratory assessments be completed as required and that the central laboratory be used for assessments whenever possible. In the event that a patient cannot return to the clinic for a scheduled or unscheduled visit, or there is an event that triggers a need for an immediate assessment, the use of a local lab is permissible at the discretion of the Investigator. In these cases, the Investigator will obtain the laboratory results and the laboratory normal ranges.

The process for assessing criteria is presented in Figure 2, and the specific threshold(s) for each laboratory analyte to trigger mandatory repeat testing and, potentially, a complete patient evaluation (depending on the repeat result) are summarized in Table 3.

Figure 2: DILI Management Algorithm

DILI = drug-induced liver injury; IP = Investigational Product

NOTE Other laboratory criteria include: ALT, AST, total bilirubin, INR, and electrolytes (sodium).

Table 3: Liver Laboratory Criteria for Monitoring of Suspected Hepatic Injury or Potential Hepatic Decompensation and Criteria for Interruption or Discontinuation of Investigational Product

A. Laboratory Criteria for Monitoring Suspected Hepatic Injury		
Laboratory Parameter	Action Taken	Rechallenging Criteria
Total Bilirubin		If a patient interrupts IP, they may be rechallenged after a minimum of 30 days if fully resolved OR stable and approved by the Medical Monitor and Investigator.
Baseline \leq ULN and \geq 3x baseline	Interrupt IP	
Baseline $>$ ULN and \geq 2x Baseline	Interrupt IP	
ALT or AST		
$>$ 3x baseline (and $>$ ULN)	Interrupt IP	
\geq 2x baseline	Repeat Test in 2 to 3 days, interrupt IP if still elevated	
Electrolytes^a		
Sodium $<$ 130 mEq/L	Repeat Test in 2 to 3 days, interrupt IP if still below limit	
B. Laboratory Criteria for Monitoring Potential Hepatic Decompensation (Absence of Clinical Symptoms)		

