9.7.6. Week 3 and Week 42 Safety Visit Procedures

Preferably, the patient will come in to the clinic for this visit. Alternatively, the site will telephone the patient for assessments and a home health nurse will visit to draw safety labs.

- Verify that patient is dosing as directed.
- Verify that the patient has fasted for at least 8 hours.
 - Record fasting status in the source and eCRF
 - If the patient reports having eaten within 8 hours, document accordingly in the source and eCRF and remind the patient that fasting is required prior to all study visits.
- Review and record prior concomitant medications.
- Assess and record AEs.
- Review and record any non-study related medical or surgical treatment procedures and any medically relevant HCP or non-HCP related office visits that have occurred since the previous study visit.

- Assess investigational product compliance, perform investigational product accountability.
- **For Week 42 Only:** Assess for dose titration, if eligible. (Refer to [Section 7.3](#))
- **For Week 42 Only:** Dispense investigational product only if there is dose increase or as needed. No new investigational product bottles will be dispensed if there is only change in dosing frequency of the same dose level. Patients are expected to use up each investigational product bottle before a new bottle will be dispensed
- Obtain blood samples for
 - Serum chemistry, hematology, and coagulation
- Schedule the next visit (Week 6 or Week 48), reiterate dosing instructions, and advise the patient:

For Week 3 Only:

- **Week 6 Visit should occur 3, 4, or 5 days after taking the Week 6 dose**, eg, if the Week 6 dose is taken on a Sunday, the patient should come in for the Week 6 Visit within the following Wednesday and Friday ([Figure 3](#)).
- NOT to take investigational product on the morning of the next visit, and
- To bring the investigational product bottle(s) to the visit
- To fast overnight (at least 8 hours) prior to the next visit. Fasting is required prior to all study visits, but water is permitted.

For Week 42 Only:

- NOT to take investigational product on the morning of the next visit, and
- To bring the investigational product bottle(s); s/he will dose at the clinic (if this is in compliance with the established dosing frequency), and
- To fast overnight (at least 8 hours) prior to the next visit. Fasting is required prior to all study visits, but water is permitted.

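### A dose raised at Week 48 or at a quarterly extension visit has no planned contact or liver tests for about 13 weeks, against about 3 weeks (contact) and 6 weeks (labs) for earlier increases

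*Protocol*

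**What the plan says.** **Titration stays open.** Footnote j to Table 1 (Section 7.1.2) reads "Dose titration of investigational product may occur starting after the Week 12 Visit, or any study visit thereafter for patients on all dosing regimens" and gives no end date. Table 1 marks the titration assessment at Weeks 12 to 48 and in the extension column. Sections 9.7.11 (Week 48) and 9.7.12 (quarterly visits) both carry the instruction "Assess for dose titration, if eligible".

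**Monitoring thins out at Week 48.** Up to then, under Section 7.1, "subsequent clinic visits will occur approximately every 6 weeks for the assessment of safety, tolerability, PK, and PD", and footnote b adds "Patients should be contacted by telephone/email every 3 weeks (±1 week) between clinic visits starting at Week 9 and continuing to Week 48". Section 9.7.8 agrees on where the calls end: "Patients should be contacted by telephone/email at Week 9 and every 3 weeks afterward to Week 48". From Week 48, Table 1 and 9.7.12 provide serum chemistry, hematology and coagulation every 3 months and list no contact between visits.

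**Extra monitoring elsewhere.** Section 7.6 sets contact at least every 2 weeks and visits every 6 weeks once product is interrupted or discontinued, and adds procedures for suspected injury or decompensation. Section 8.4 calls for more frequent monitoring on rechallenge, without an interval. Section 7.4.2 allows unscheduled labs prompted by symptoms or a laboratory alert. Section 9.7.14 leaves unscheduled visits to the investigator's judgment. None of these is triggered by an ordinary dose increase.

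**The concern.** The schedule relaxes at the point where it would suit a patient on a stable dose, but dose increases remain permitted. Labs taken on the day of an increase reflect the old dose. The first values that reflect the new dose come at the next planned draw.

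Patients are told to report symptoms (7.4.1), so the exposed case is the silent one. Table 3 Part B is written for rises without clinical symptoms: bilirubin up by 1.5 mg/dL (baseline at or below ULN) or 1.0 mg/dL (baseline above ULN), or INR up by more than 0.3. Those triggers, and the interruption and discontinuation thresholds in the rest of Table 3, work only on blood that has been drawn.

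The protocol itself argues for the opposite emphasis. Section 5.5 justifies more extensive monitoring by the raised risk of decompensation and possible higher hepatic exposure in this population, and Section 5.6 says progression can be rapid. Under 7.6, a patient taken off drug is contacted at least every 2 weeks, whereas a patient whose dose has just been raised in the extension has nothing planned for a quarter of a year.

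**Working it through.** No power or sample-size figure is involved. The check is interval arithmetic on Table 1.

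**Inputs**
- Visits and labs at Weeks 12, 18, 24, 30, 36, 42 and 48, window ±1 week (Table 1).
- Extension visits and labs every 3 months, window ±2 weeks (Table 1). Three months = 365.25 / 4 / 7 = 13.04 weeks, taken as 13.
- Contacts every 3 weeks from Week 9 to Week 48 (footnote b, 9.7.8).
- Both titration steps are twice-weekly regimens: 5 mg, then 10 mg (Table 2).

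**Time to the next planned labs and contact.** Visits are anchored to Day 1 (9.7.1), so the windows at both ends add: gap ± (window at the increase + window at the next draw).

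| Increase made at | Labs, nominal | Labs, with windows | Contact, nominal |
|---|---|---|---|
| Weeks 12 to 42 | 6 weeks | 6 ± (1 + 1) = 4 to 8 | 3 weeks |
| Week 48 | 13 weeks | 13 ± (1 + 2) = 10 to 16 | 13 weeks |
| Extension visit | 13 weeks | 13 ± (2 + 2) = 9 to 17 | 13 weeks |

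The nominal ratio for labs is 13 / 6 = 2.2.

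**Doses taken on the new regimen before the first planned labs**, at 2 per week:
- Weeks 12 to 42: 2 × 6 = 12 (2 × 4 = 8 to 2 × 8 = 16).
- Week 48: 2 × 13 = 26 (2 × 10 = 20 to 2 × 16 = 32).
- Extension visit: 26 (2 × 9 = 18 to 2 × 17 = 34).

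**Total intake over the nominal gap**
- Step to 5 mg twice weekly: 12 × 5 = 60 mg versus 26 × 5 = 130 mg.
- Step to 10 mg twice weekly: 12 × 10 = 120 mg versus 26 × 10 = 260 mg.

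Each step doubles the weekly dose (5 to 10 mg, then 10 to 20 mg), so the part due to the increase is half of these totals: 30 versus 65 mg, and 60 versus 130 mg.

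**Does the 24-hour PK sample after Week 48 fill the gap?** No. Section 7.3 starts the higher regimen no earlier than 2 days after the previous dose, and the Week 48 dose is given in clinic that day, so the 24-hour sample precedes the new regimen.

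**How many patients?** The protocol does not say. Six titration visits (Weeks 12, 18, 24, 30, 36, 42) precede Week 48. With steps at least 6 weeks apart, both can be done by Week 18.

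**The case against.** The strongest reply is that nothing here is contradictory. Table 1, 9.7.11 and 9.7.12 agree with one another, a tapered extension schedule is a legitimate choice, and the Version 3 summary of changes, which introduced the hepatic monitoring rules, states that extension visits were left as they were. That makes an oversight less likely. It does not explain why an increase at Week 42 gets labs at 6 weeks and one at Week 48 gets them at 13.

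Several narrower points have force:

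- **Few patients.** The group is mainly those held below the maximum dose through Week 48 and then raised. For re-escalation after rechallenge, the wording in 8.4 arguably applies, although it gives no interval. This limits the size of the problem but does not remove it.
- **First action under Part B.** For a Part B bilirubin or INR rise, the first action is close monitoring, with interruption only if values keep climbing. A patient found at 6 weeks might therefore stay on the dose at first. That is correct, but the close monitoring also has to be started by a drawn value, as do the Part A interruption rules and the permanent stop at INR 2.0 or above.
- **Milligrams.** Total intake overstates the added exposure, which is half as large, and cumulative milligrams are not shown to track hepatic risk. The intervals are the better measure.
- **Worst case.** The 16- and 17-week gaps need both visits at opposite ends of their windows. The nominal 13 weeks does not.
- **Other safeguards.** Section 5.5 promises frequent assessment by the investigator and Medical Monitor, 7.4.1 asks patients to report outside care and tests, and 9.7.14 allows extra visits. These help, but none fixes a date for a call or a draw.

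**Conclusion.** The concern holds. For an ordinary up-titration at Week 48 or later, the first planned contact moves from about 3 to about 13 weeks and the first planned labs from 6 (4 to 8) to 13 weeks (10 to 16, or 9 to 17 between extension visits). No other section closes that interval for a patient without symptoms.

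This is a gap in safety monitoring in a high-risk population. It is not an internal contradiction, and it does not affect any planned analysis. The conclusion rests on reading 3 months as 13 weeks and on the discretionary and symptom-triggered provisions not counting as planned follow-up. The number of patients is unknown and probably small, but it need not be zero: titration is optional and depends on tolerability, and blinded treatment continues until all patients have finished 48 weeks and the database is locked, which the protocol puts at approximately 3 years. The change should be made because it is cheap and the exposed patients are vulnerable.

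**What to change.** Add to Table 1 (Week 48 and extension columns) and to Sections 9.7.11 and 9.7.12: any up-titration at or after Week 48 is followed by one telephone contact at about 3 weeks and one serum chemistry and coagulation draw at about 6 weeks. This restores the follow-up given after increases at Weeks 12 to 42. The means already exist in Section 9.7.6 for Weeks 3 and 42: "Alternatively, the site will telephone the patient for assessments and a home health nurse will visit to draw safety labs".

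The cost is amendment wording plus one call and one draw per late up-titration. Patients on a stable dose keep the quarterly schedule, and no endpoint or analysis changes.
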